2.4.2 Prior, concomitant and post therapies

Prior and concomitant treatments will be summarized by treatment group for the Safety Set unless otherwise specified. Concomitant treatments will be displayed for the treatment period 1 and entire treatment period.

Prior medications are defined as drugs taken and stopped prior to first dose of study treatment.

Concomitant medications are defined as any medication administered at least once between the day of first dose and the last day of study visit, other than study medication, including those which were started pre-baseline and continued into the treatment period.

Any medication administered during the six months prior to study enrollment will be considered as prior and concomitant medication.

Medications will be identified and presented in alphabetical order, using Novartis drug and therapy dictionary (NovDTD) and by Anatomical Therapeutic Chemical (ATC) codes and grouped by anatomical main group (the first level of the ATC codes).

Prior and concomitant treatments will be summarized by treatment group using frequency count and percentages for the Safety Set, unless otherwise specified.

Table will also show the overall number and percentage of patients receiving at least one drug of a particular ATC code and at least one drug in a particular anatomical main group.

In addition, medical procedures and significant non-drug therapies as coded in MedDRA will be summarized.

SAP 0

Treatment used, dose and date of administration will be listed. Duration of exposure will be presented by treatment if treatment is stopped during study period. Ongoing treatments will be flagged.

Page 18

Prior or concomitant medication will be identified based on recorded or imputed start and end dates of medication taken. Further rules will be given in Section 5.1.3.

2.5 Analysis of the primary objective

2.5.1 Primary endpoint

The primary efficacy variables are the response of psoriasis skin lesions to treatment as measured by:

- a) Response in skin histology/K16 expression to treatment (yes, no) (at Week 12)
- b) PASI 90 (yes, no) (at Weeks 4, 8, and 12)

The primary analysis time point will be at Week 12.

2.5.1.1 Definition of PASI and related variables

The investigator or trained qualified designee will complete the PASI assessments. Whenever possible, the same evaluator should perform this assessment at all visits.

The total BSA affected by plaque-type psoriasis will be estimated from the percentages of areas affected, including head, trunk, upper limbs and lower limbs (see below for PASI assessment). The following calculations will be done: each reported percentage will be multiplied by its respective body region corresponding factor (head = 0.1, trunk = 0.3, upper limbs = 0.2, lower limbs = 0.4). The resulting 4 percentages will be added up to estimate the total BSA affected by plaque-type psoriasis. The PASI scoring system is further described in Table 2-5.

A PASI score will be derived as indicated in Table 2-5. The head, trunk, upper limbs and lower limbs are assessed separately for erythema, thickening (plaque elevation, induration), and scaling (desquamation). The average degree of severity of each sign in each of the four body regions is assigned a score of 0-4. The area covered by lesions on each body region is estimated as a percentage of the total area of that particular body region. Further practical details help the assessment:

- 1. The neck is assessed as part of the head.
- 2. The axillae and groin are assessed as part of the trunk.
- 3. The buttocks are assessed as part of the lower limbs.
- 4. When scoring the severity of erythema, scales should not be removed.

Because the head and neck, upper limbs, trunk and lower limbs correspond to approximately 10%, 20%, 30% and 40% of the body surface area, respectively, the PASI score will be calculated using the formula:

 $PASI = 0.1 \ (E_h + I_h + D_h)A_h + 0.2 \ (E_u + I_u + D_u)A_u + 0.3 \ (E_t + I_t + D_t)A_t + 0.4 \ (E_l + I_l + D_l)A_{l,1} + 0.1 \ (E_l + I_u + D_u)A_{l,2} + 0.1 \ (E_l + I_u + D_u)A_{l,3} + 0.1 \ (E_l + I_u + D_u)A_{l,4} + 0.1$

where E, I, D, and A denote erythema, induration, desquamation, and area, respectively, and h, u, t, and l denote head, upper extremities, trunk, and lower extremities, respectively (see Table 2-5).

PASI scores can range from a lower value of 0, corresponding to no signs of psoriasis, up to a theoretic maximum of 72.0.

The investigator is responsible for collecting the components or scoring signs and total regional area for all visits. PASI and total BSA calculations will be done by investigator at screening and randomization only; The PASI scores after randomization will be calculated by Novartis and will be used in the analysis and for derivation of PASI response values (see below).

Table 2-5 The PASI scoring system

I able 2-3	The FASI scoring system				
Body region	Erythema (E)	Thickening (plaque elevation, induration, I)	Scaling (desquamation, D)	Area score (based on true area %, A)*	
Head (H) [†]	0=none 1=slight 2=moderate 3=severe 4=very severe	0=none 1=slight 2=moderate 3=severe 4=very severe	0=none 1=slight 2=moderate 3=severe 4=very severe	0 = no involvement 1 = >0-<10% 2 = 10-<30% 3 = 30-<50% 4 = 50-<70% 5 = 70-<90% 6 = 90-100%	
Trunk (T)‡	0=none 1=slight 2=moderate 3=severe 4=very severe	0=none 1=slight 2=moderate 3=severe 4=very severe	0=none 1=slight 2=moderate 3=severe 4=very severe	0 = no involvement 1 = >0-<10% 2 = 10-<30% 3 = 30-<50% 4 = 50-<70% 5 = 70-<90% 6 = 90-100%	
Upper limbs (U)	0=none 1=slight 2=moderate 3=severe 4=very severe	0=none 1=slight 2=moderate 3=severe 4=very severe	0=none 1=slight 2=moderate 3=severe 4=very severe	0 = no involvement 1 = >0-<10% 2 = 10-<30% 3 = 30-<50% 4 = 50-<70% 5 = 70-<90% 6 = 90-100%	
Lower limbs (L)§	0=none 1=slight 2=moderate 3=severe 4=very severe	0=none 1=slight 2=moderate 3=severe 4=very severe	0=none 1=slight 2=moderate 3=severe 4=very severe	0 = no involvement 1 = >0-<10% 2 = 10-<30% 3 = 30-<50% 4 = 50-<70% 5 = 70-<90% 6 = 90-100%	

^{*} Percentage (not score) of body region (not whole body) affected will be entered in the eCRF.

[†] Neck is assessed as part of the Head (H) body region.

- [‡] Axillae and groin are assessed as part of the Trunk (T) body region.
- § Buttocks are assessed as part of the Lower limbs (L) body region.

The following definitions are possible efficacy evaluations that can be used in clinical trials in psoriasis:

• PASI 90 response: patients achieving ≥ 90% improvement (reduction) in PASI score compared to baseline are defined as PASI 90 responders

2.5.2 Statistical method of analysis

• Response of skin histology/K16 expression to treatment (yes, no) (at Week 12)

Difference between the two treatment groups –(secukinumab 300 mg versus placebo) with respect to percentage of patients who have a negative ("no") response to skin histology/keratin 16 to treatment at Week 12, will be presented along with 95% confidence interval. Confidence interval will be calculated using normal approximation to the binomial distribution.

• PASI 90 (yes, no) (at Weeks 4, 8, and 12)

Same method of analysis as described above will be used for PASI 90 response (yes, no) at Weeks 4, 8, and 12.

The primary analysis of the primary efficacy variables will be based on the Full Analysis Set.

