## Table 3-1Clinical outcomes at Week 12 in adults with plaque psoriasis in Trials1-4

	Trial 1		Trial 2	2	Trial 3	}	Trial 4	ــــــــــــــــــــــــــــــــــــ
	Secukinumab 300 mg (N=245) n (%)	Placebo (N=248) n (%)	Secukinumab 300 mg (N=327) n (%)	Placebo (N=326) n (%)	Secukinumab 300 mg (N=59) n (%)	Placebo (N=59) n (%)	Secukinumab 300 mg (N=60) n (%)	Placebo (N=61) n (%)
PASI 90 response	145 (59)	3 (1)	175 (54)	5 (2)	35 (60)	0 (0)	33 (55)	0 (0)
IGA of clear or almost clear	160 (65)	6 (2)	202 (62)	9 (3)	40 (68)	0 (0)	44 (73)	0 (0)

Examination of age, gender, and race subgroups did not identify differences in response to secukinumab among these subgroups.

PASI 90 response at Week 12 was achieved with secukinumab 300 mg and 150 mg compared to placebo in 59% (145/245) and 39% (95/245) versus 1% (3/248) of subjects, respectively (Trial 1) and 54% (175/327) and 42% (137/327) versus 2% (5/326) of subjects, respectively (Trial 2). Similar results were seen in Trials 3 and 4.

With continued treatment over 52 weeks, subjects in Trial 1 who were PASI 75 responders at Week 12 maintained their responses in 81% (161/200) of the subjects treated with secukinumab 300 mg. Trial 1 subjects who were clear or almost clear on the IGA at Week 12 also maintained their responses in 74% (119/160) of subjects treated with secukinumab 300 mg. Similarly in Trial 2, PASI 75 responders maintained their responses in 84% (210/249) of subjects treated with secukinumab 300 mg. Trial 2 subjects who were clear or almost clear on the IGA also maintained their responses in 80% (161/202) of subjects treated with secukinumab 300 mg.

Among the subjects who chose to participate (39%) in assessments of patient reported outcomes, improvements in signs and symptoms related to itching, pain, and scaling, at Week 12 compared to placebo (Trials 1 and 2) were observed using the Psoriasis Symptom Diary©.

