### 9.4.2 Statistical model, hypothesis, and method of analysis

For the two primary efficacy variables at each time point (response in skin histology/K16 expression to treatment at Week 12, PASI 90 at Weeks 4, 8, and 12), 95% confidence interval

for the difference between the two treatment groups with respect to the percentage of patients who have the "event" will be calculated using the normal approximation to the binomial distribution.

The primary analysis of the primary efficacy variables will be based on the Full Analysis Set.

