## 9.8 Sample size calculation

The table below considers total sample sizes of 75 patients (50 in secukinumab group and 25 in placebo group) and 99 patients (66 in secukinumab group and 33 in placebo group) to estimate the difference between the two groups with respect to the pooled estimate of the two percentages of patients who have the "event" at Week 12 for each of the two primary efficacy variables. The entries in the table are the "margin of error" (half-width of confidence interval) for a two-sided 95% confidence interval (Julious and Patterson, 2004; Kianifard and Islam, 2011; nQuery Advisor 7.0).

Sample size calculations for percentage of patients who have the

Confidential

"event"				
Percentage with "event"	Half-width of confidence interval for $n = 75$	Half-width of confidence interval for $n = 99$		
30%	25.0%	21.4%		
40%	26.5%	22.7%		
50%	27.0%	23.2%		
60%	26.5%	22.7%		
70%	25.0%	21.4%		

Based on the results in the above table, it was decided that approximately 75 randomized patients (50 in secukinumab group and 25 in placebo group) will be randomized in this exploratory study to estimate the difference in response rates between the two treatment groups.

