1.1 Study design

This study uses a randomized, double-blind, placebo-controlled, parallel-group, multicenter design. The study consists of five periods:

- Screening (from 1-4 weeks before randomization);
- Double-blind Treatment Period (Randomization to Week12 pre-dose);
- Double-blind Induction Period (Week 12 post dose to Week 15 dose);
- Open-label Treatment Period (Week 16 to Week 52); and
- Follow-up Period (1 week).

A schematic of the study design is presented below:

Approximately 75 moderate to severe plaque psoriasis patients (50 in secukinumab group and 25 in placebo group) from approximately 15 sites will be randomized at Visit 2/Baseline in a 2:1 ratio

to receive secukinumab 300 mg or placebo, respectively. Randomization will be stratified by body weight collected at Visit 2 (<90 kg or ≥90 kg).

An interim analysis is planned after Week 12, which is the primary analysis time point for the study. Interim analysis will be performed after all patients have completed the Week 12 visit and the database is locked.

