5.4 Statistical models

5.4.1 Primary analysis

No formal hypothesis will be tested.

Treatment difference will be calculated in terms of proportion of response along with 95% CI using normal approximation of binomial distribution.

Sample SAS code:

Novartis For business use only Page 34 SAP 0

Sensitivity analysis:

Sample SAS Code:

Logistic regression model with treatment and body weight (<90 kg, >=90 kg) as explanatory variables.

```
proc logistic data=xxx descending;
  class treatment weight/ param=glm ;
  model <response var> =treatment weight;
  contrast 'trtA vs. trtB ' treatment 1 -1 ;
  run;
```

Logistic regression model with treatment and body weight (<90 kg, >=90 kg) and treatment-by-body weight(<90kg, >=90kg) as explanatory variables.

```
proc logistic data=xxx descending;
  class treatment weight/ param=glm ;
  model <response var> =treatment weight treatment*weight;
  contrast 'A vs B in wgt=1 (<90)' treatment 1 -1 treatment*wgt 1 0 -1 0
/estimate=exp;
  contrast 'A vs B in wgt=1 (>=90)' treatment 1 -1 treatment*wgt 0 1 0 -1
/estimate=exp;
run;
```

Note: 'descending' option is used if Yes is coded as 1 and No is coded as 0

if Yes is coded as 1 and No is coded as 2 then no option is requesired

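### The primary 95% CI is an unspecified normal approximation with no zero-cell rule, although no placebo PASI 90 responders is the likeliest result; naming a score interval is a cheap improvement

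*SAP*

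**What the plan says.** Three places define the primary interval, in nearly the same words:

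- SAP 2.5.2, for K16 and, by cross-reference, for PASI 90 at Weeks 4, 8 and 12: "Confidence interval will be calculated using normal approximation to the binomial distribution".
- Protocol 9.4.2: the interval "will be calculated using the normal approximation to the binomial distribution".
- SAP 5.4.1: "Treatment difference will be calculated in terms of proportion of response along with 95% CI using normal approximation of binomial distribution".

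None states whether the variance is pooled or unpooled, whether a continuity correction applies, or what happens with a zero cell or a limit outside the possible range. SAP 5.4.1 announces sample code, but code for this interval does not appear in the text available.

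Both documents plan 50 secukinumab and 25 placebo patients. Protocol Table 3-1 and the text below it give Week 12 PASI 90 for the 300 mg dose, the 150 mg dose and placebo in Trial 1 as "59% (145/245) and 39% (95/245) versus 1% (3/248) of subjects". Across the four trials the 300 mg rate is 54-60% and the placebo rate 0-2%. Neither document gives an expected K16 rate, or a PASI 90 rate at Week 4 or 8.

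SAP 5.4.1 says that no formal hypothesis is tested. SAP 2.5.4 adds a logistic regression, which is dropped if the data are separated or quasi-separated.

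**The concern.** The normal approximation is weakest when an arm is small and its event rate is close to 0% or 100%. The placebo arm for PASI 90 is exactly that case. If no placebo patient responds, the usual unpooled variance estimate for that arm is zero, and the interval treats the placebo rate as if it were known.

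Because the study tests nothing, this interval is the primary inference. The same zero cell also produces the quasi-separation that cancels the logistic analysis in SAP 2.5.4, so the planned support would probably be missing just when the primary interval is least reliable.

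There is also a plain gap in specification. Two programmers could follow the text correctly and report different limits.

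**Working it through.** **Inputs.** n = 50 and 25, two-sided 95% (SAP 1.1; Protocol 9.8). Secukinumab PASI 90 54-60%. Placebo 3/248, 5/326, 0/59 and 0/61, together 8/694 = 1.15% (Protocol Table 3-1). Missing PASI 90 counts as non-response (SAP 2.5.3), so the denominators stay near 50 and 25.

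**1. The plan's own figures.** Protocol 9.8 tabulates the "half-width of confidence interval) for a two-sided 95% confidence interval". They are reproduced by

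half-width = 1.96 × √[p(1−p)(1/n₁+1/n₂)] + ½(1/n₁+1/n₂).

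For 50 and 25, 1/n₁+1/n₂ = 0.06. At p = 50% this gives 1.96 × √(0.25 × 0.06) + 0.03 = 0.240 + 0.030 = 27.0%, as printed. All ten entries match. Without the last term, the continuity correction, none does: n = 75 gives 22.0, 23.5, 24.0, 23.5 and 22.0%. So the planning used a correction that the analysis text does not mention. The table covers only pooled rates of 30-70%.

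**2. Chance of a zero placebo cell.** The expected number of events at 1.15% is 25 × 0.0115 = 0.29. P(0/25) = (1 − 8/694)²⁵ = 0.748. At 1% it is 0.99²⁵ = 0.78, and at 2% it is 0.98²⁵ = 0.60.

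**3. A typical result, 28/50 versus 0/25.** Uncorrected, unpooled: 0.56 ± 1.96 × √(0.56 × 0.44/50 + 0) = 0.56 ± 0.138.

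| Method | 95% CI |
|---|---|
| Normal, uncorrected | 42.2 to 69.8% |
| Normal, corrected (± 0.03 more) | 39.2 to 72.8% |
| Miettinen-Nurminen score | 40.8 to 68.9% |
| Newcombe | 36.9 to 68.8% |

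**4. Exact coverage, Week 12 PASI 90.** For each pair of true rates, the binomial probabilities of all 51 × 26 outcomes whose interval contains the true difference are summed. Over 54-60% versus 1-2%:

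| Method | Coverage |
|---|---|
| Normal, uncorrected | 93.2-95.3% |
| Normal, corrected | 97.0-98.2% |
| Miettinen-Nurminen | 94.9-96.5% |
| Newcombe | 95.8-97.3% |

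The uncorrected shortfall comes mostly from the lower limit. That limit lies above the true difference 2.6% of the time at 54% versus 1%, and 4.8% of the time at 57% versus 2%, against a nominal 2.5%. At these rates an impossible limit has probability of at most about 5 × 10⁻⁸, and a zero-width interval about 6 × 10⁻¹².

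**5. Rates the documents do not give (assumptions).** K16 event rate on secukinumab, with placebo set at 1.15%:

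| Secukinumab | Uncorrected | Corrected | Miettinen-Nurminen |
|---|---|---|---|
| 80% | 91.1% | 98.2% | 96.7% |
| 90% | 91.1% | 97.4% | 96.1% |
| 95% | 78.9% | 94.2% | 95.9% |
| 98% | 72.7% | 72.7% | 95.8% |

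With placebo at 2%, the uncorrected upper limit exceeds 100% with probability 0.5%, 23% and 67% at 80%, 90% and 95% on secukinumab. An example is 48/50 versus 1/25: 82.6 to 101.4%, against a score interval of 75.4 to 97.3%.

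Early PASI 90 with placebo at 1% and secukinumab at 2%, 5% or 10%: the uncorrected interval has zero width with probability 28%, 6% and 0.4%, and coverage is 71%, 91% and 96%. For 0/50 versus 0/25 it is 0 to 0, against a score interval of −13.5 to 7.2%.

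**The case against.** A reader might infer that the primary interval is badly miscalibrated, or likely to be impossible or of zero width. The documents do not support that, for four reasons.

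- **The uncorrected form is a reading, not a statement.** The planning half-widths include the correction, and the missing sample code may have named it. With it, Week 12 PASI 90 coverage is above 95%. This stands, so the undercoverage is conditional. What remains either way is that the analysis text does not identify the interval.
- **For the one endpoint with documented rates, the effect is small.** The shortfall is at most about 2 points and absent at some rates (95.3% at 54% versus 1%). At 28/50 versus 0/25 the lower limit moves by 1.4 points, and no conclusion changes. This stands.
- **The large failures rest on assumed rates.** SAP 2.5.2 analyses the K16 result 'no', while SAP 2.5.3 scores missing K16 as 'yes'. Each missing biopsy in 50 therefore takes 2 points off the event rate, and 95-98% would be extreme. The 72.7% for the corrected interval is also a knife edge: the true difference of 96.85% lies just below the corrected lower limit of 97.0% for 50/50 versus 0/25, and at 98% versus 1% coverage is 100%. Weeks 4 and 8 are not the primary time point. All of this stands.
- **Nothing is decided by the interval.** The study is exploratory and tests no hypothesis, so whether a limit excludes zero has no formal role. This limits the severity, but the interval remains the reported measure of precision.

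The correction is still not a full answer. It is conservative at the documented rates, and it can still pass 100%: 48/50 versus 1/25 becomes 79.6 to 104.4%.

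**Conclusion.** The point holds as a gap in specification with a modest effect on calibration. The plan names a family of intervals, not one interval, for an arm where a zero count has a probability of roughly 60-78%, and it has no sparse-data rule.

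For Week 12 PASI 90, coverage is about 93.2-95.3% if no correction is applied and about 97-98% if the planning correction is applied. Impossible or zero-width limits are negligible there. They, and the serious undercoverage, arise only if K16 rates are extreme or early PASI 90 rates are near zero, and the documents give no basis for expecting either.

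This is a cheap improvement of minor to moderate severity, not a condition for going ahead. The figures assume exactly 50 and 25 patients, independent binomial counts, an unpooled variance in the analysis, and placebo rates like those in Table 3-1.

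**What to change.** In SAP 2.5.2 and 5.4.1, and in Protocol 9.4.2 if it is amended, replace the normal approximation by the Miettinen-Nurminen score 95% CI for the treatment difference. Apply it to both primary variables and all time points. It handles zero cells and stays within the possible range, so no separate rule is needed.

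Another score-type interval such as Newcombe is also acceptable. It covers 95.8-97.3% at the documented PASI 90 rates, though 92.2% at an assumed 95% versus 2%.

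If the protocol is not amended, record the change in SAP Section 4, which now lists none. The within-stratum analyses need no change on this account, because SAP 2.5.4 reports odds ratios with their own intervals there.

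The cost is one SAP sentence and one option in the frequency procedure, with no extra patients or data. The downside is intervals slightly wider than, or shifted from, the uncorrected normal ones, mainly a lower limit further from the estimate.

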2.5.3 Handling of missing values/censoring/discontinuations

For the primary efficacy variable K16 expression to the treatment at Week 12 (and other time points), a patient with a missing assessment will be considered as having a positive ("yes") response regardless of the reason for missing data (e.g., premature study discontinuation, missed visit, administrative issues). Patients who discontinue the trial for any reason will be considered as having a positive ("yes") response from the time they drop out through Week 52.

For the primary efficacy variable PASI90 response at Week 12 (and other time points), a patient with a missing assessment will be considered as a non-responder regardless to the reason for missing data (e.g., premature study discontinuation, missed visit, administrative issues). Patients who discontinuethe trial for any reason will be considered non-responders from the time they drop out through Week 52.

2.5.4 Supportive analyses

Sensitivity analyses will be performed as follows:

The two primary efficacy variables will be analyzed at each time point (as describe in section 2.5.1) with non-responder imputation using a logistic regression model with treatment and body weight (< 90 kg, ≥90kg) as explanatory variables (Stokes, Davis, and Koch, 2012). The odds ratio and 95% confidence intervals for odds ratios (secukinumab 300 mg versus placebo) based on the fitted model will be reported.

In addition, estimates of differences between the two proportions within each stratum will be calculated using treatment-by-stratum interaction in the above model, separately. The odds ratio and 95% confidence intervals for odds ratios will be reported to examine meaningful treatment difference by strata.

This logistic regression analysis will not be performed if the data is sparse (quasi-separated or completely separated).

The sensitivity analysis will be done based on the Full Analysis Set.

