### 9.4.4 Sensitivity analyses

The two primary efficacy variables will be analyzed at each time point for the Full Analysis Set using a logistic regression model with treatment and body weight (<90 kg,  $\geq$ 90 kg) as explanatory variables (Stokes, Davis, and Koch, 2012). The odds ratios and 95% confidence intervals for the odds ratios based on the fitted model will be reported.

Estimates of differences between the two proportions within each stratum will be calculated and examined for meaningful treatment-by-stratum interaction.

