2.1 Data analysis general information

Novartis will perform the statistical analysis.

Data will be analyzed by the statistical software SAS, Version 9.4 according to Section 9 (Data Analysis) of the study protocol which will also be available in Appendix 16.1.1 of the Clinical Study Report (CSR). Important information is given in the following sections and details are provided, as applicable, which will also be in Appendix 16.1.9 of the CSR.

Data up to Week 12 will be presented for the Week 12 interim analysis and all data will be presented for final analysis.

It is planned that the data from all centers that participate in this protocol will be combined, so that an adequate number of patients will be available for analysis.

Summary statistics for continuous variables will include n, mean, standard deviation, standard error of the mean, minimum, lower quartile, median, upper quartile, interquartile range, and maximum.

Summary statistics for discrete variables will be presented in contingency tables and will include frequencies and percentages.

Primary efficacy variables will be summarized for lesional samples.

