2.2.1 Subgroup of interest

The primary efficacy variables and efficacy variables will be evaluated using randomization weight strata: "body weight <90 kg", "body weight ≥90 kg".

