2.14 Interim analysis

The database of this study will be locked twice, first after the end of double-blind treatment period (Week 12) and again at the end of the follow-up period (Week 53). Data analyses will follow each database lock. The main analysis for the primary objective will be done at Week 12. As Week 12 analysis considered primary and no specific hypothesis is preidentified for testing, adjustment of significance level due to this interim analysis is irrelevant.

3 Sample size calculation

The table below considers total sample sizes of 75 patients (50 in secukinumab group and 25 in placebo group) and 99 patients (66 in secukinumab group and 33 in placebo group) to estimate the difference between the two groups with respect to the pooled estimate of the two percentages of patients who have the "event" at Week 12 for each of the two primary efficacy variables. The table shows "margin of error" (half-width of confidence interval) for a twosided 95% confidence interval (Julious and Patterson, 2004; Kianifard and Islam, 2011; nQuery Advisor 7.0).

0

Based on the results in the above table, it was decided that approximately 75 randomized patients (50 in secukinumab group and 25 in placebo group) will be randomized in this exploratory study to estimate the difference in response rates between the two treatment groups.

4 Change to protocol specified analyses

Not applicable.

5 Appendix

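### The only weight-adjusted PASI 90 effect is a logistic model that the SAP cancels under separation with no fallback; at the earlier trials' placebo rate this happens in about 75% of trials at Week 12.

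*SAP*

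**What the plan says.** Protocol 5.3.1 stratifies randomisation by body weight, below 90 kg against 90 kg or more. Protocol 9.4.2 and SAP 2.5.2 define the primary PASI 90 analysis as a simple difference in percentages at Weeks 4, 8 and 12, without weight: "Confidence interval will be calculated using normal approximation to the binomial distribution".

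Weight enters the treatment effect in SAP 2.5.4, as a covariate in a supportive logistic regression on treatment and weight stratum. The same section sets the cancel rule: "This logistic regression analysis will not be performed if the data is sparse (quasi-separated or completely separated". The code in SAP 5.4.1 is ordinary maximum-likelihood logistic regression, and its second model is "model <response var> =treatment weight treatment*weight". Neither place names an alternative for use when the model is dropped.

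On results by stratum, Protocol 9.4.4 says: "Estimates of differences between the two proportions within each stratum will be calculated and examined for meaningful treatment-by-stratum interaction". SAP 2.5.4 says these differences will be "calculated using treatment-by-stratum interaction in the above model, separately", and that odds ratios will be reported. SAP 2.1 says the data are analysed "according to Section 9 (Data Analysis) of the study protocol". SAP 2.2.1 says the primary variables "will be evaluated using randomization weight strata", without giving a method. Under the heading "4 Change to protocol specified analyses" the SAP enters not applicable.

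**The concern.** A rule that withholds an inestimable odds ratio is reasonable. The difficulty is that the condition triggering it is the expected one for PASI 90. The protocol's summary of earlier trials shows almost no placebo responders at Week 12, and this trial plans only 25 placebo patients. Followed as written, the SAP would usually leave one of its two primary variables with no estimate that uses the stratification factor. Any substitute chosen after the Week 12 unblinding of the analysis team would be post hoc.

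There is also a mismatch that does not depend on any placebo rate. The protocol promises within-stratum differences in proportions with no cancel rule. The SAP takes them from a logistic interaction model, which yields odds ratios, and that model fails even more often than the main-effects one.

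**Working it through.** **The plan's own precision figure.** Protocol 9.8 gives 95% half-widths for 50 against 25 patients. They reproduce as 1.96·√[p(1−p)(1/50 + 1/25)] + 0.5·(1/50 + 1/25). At p = 30% this is 22.0 + 3.0 = 25.0 points, and at 50% it is 24.0 + 3.0 = 27.0 points. All ten entries, including those for 99 patients, match to 0.1 point with this continuity correction. The table is sound, but it covers pooled rates of 30% to 70% and does not address an arm with almost no events.

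**Inputs** (Protocol 3.6.1, Table 3-1, Week 12 PASI 90)
- Placebo: 3/248, 5/326, 0/59, 0/61, total 8/694 = 1.15%. Exact (Clopper-Pearson) 95% limits: 0.50% to 2.26%.
- Secukinumab 300 mg: 145/245, 175/327, 35/59, 33/60, total 388/691 = 56.2%.
- Planned arms: 50 and 25. Missing PASI 90 counts as non-response (SAP 2.5.3), so missing data cannot create a placebo responder.
- Assumption: the weight split is not given, so placebo splits of 12/13, 8/17 and 6/19 were used.

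**Main-effects model.** With no placebo responder, the maximum-likelihood treatment coefficient is infinite, which is quasi-separation. The probability is (1 − p)^25:

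| Placebo rate | P(0 of 25) |
|---|---|
| 8/694 (pooled) | 74.8% |
| 3/248 (Trial 1) | 73.8% |
| 5/326 (Trial 2) | 67.9% |
| 0.50% (lower limit) | 88.2% |
| 2.26% (upper limit) | 56.5% |

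Full enumeration of the four treatment-by-weight cells, with a linear-programming test for separation in each pattern, gives the same 74.8%. Other separation patterns add at most about 0.0002.

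**Interaction model.** This model is saturated, so it separates whenever any one of the four cells has no responders or only responders. With a 12/13 placebo split and q = 1 − 8/694, q^12 = 0.870 and q^13 = 0.860. The chance that at least one placebo cell is empty is 1 − (1 − 0.870)(1 − 0.860) = 98.2%. The other splits give up to 98.7%. Over the limits of the rate, the range is 93.8% to 99.7%.

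**What remains estimable.** Take 15/25 and 13/25 responders on secukinumab against 0/12 and 0/13 on placebo. Both logistic models are cancelled.
- Unadjusted difference: 28/50 − 0/25 = 56.0%, with 1.96·√(0.56 × 0.44/50) = 13.8 points, giving 42.2 to 69.8.
- Weight-stratified difference: Mantel-Haenszel weights are 25·12/37 = 8.11 and 25·13/38 = 8.55. The estimate is (8.11 × 0.60 + 8.55 × 0.52)/16.66 = 55.9%. The stratified Miettinen-Nurminen 95% interval is 40.3 to 68.9.
- By stratum, with score intervals: 60% (31.8 to 76.8) and 52% (25.5 to 70.2).
- Firth odds ratio: 62 (7.9 to 8077), so the upper limit is nearly uninformative.

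With uneven strata (10/17 and 18/33 against 0/8 and 0/17) the stratified difference is 55.9% (40.6 to 68.9). Exact coverage of the stratified interval at the pooled rates is 96.2%. It is 96.7% to 96.9% if the strata differ by 20 points on secukinumab.

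**The case against.** The strongest reply is that little depends on this output. In the example above, adjustment moves the estimate from 56.0% to 55.9%. In simulation at these rates, adjusted and unadjusted differences were 0.15 point apart on average. With uneven strata and an assumed 20-point stratum effect on secukinumab, the average gap was 0.3 point and the largest 1.0. Stratified randomisation already balances weight, the study is exploratory, and no hypothesis is tested. That stands, and it is why the point is minor.

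By-stratum differences are also not lost. Protocol 9.4.4 promises them, SAP 2.1 defers to Protocol Section 9, and the cancel sentence refers to the logistic regression, not to stratum proportions. This stands too: the 98% figure concerns only the interaction-model odds ratios. The wording of SAP 2.5.4 still points to the wrong route for those differences.

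One may read the cancel rule as a detail of execution that Section 4 need not list. That is arguable for the rule itself. It is less convincing for the move from differences in proportions to model-based odds ratios.

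Finally, some text is not public: Protocol 9.6, SAP 2.12 and 2.13, and the primary-analysis code in SAP 5.4.1. A stratified analysis could sit there, so the statement is limited to the text available. None of these replies supplies a prespecified weight-adjusted estimate for the case in which the model is dropped.

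**Conclusion.** The concern holds, as a minor point about supportive output. At the earlier trials' pooled placebo rate, the only weight-adjusted PASI 90 estimate at Week 12 would be cancelled in 74.8% of trials. The figure stays above half (56.5%) even at the upper exact limit of that rate. It assumes 25 placebo patients and that the earlier rates carry over; they are reported results, not a stated planning assumption. The main-effects figure barely depends on the weight split. The interaction figure of 98.2% to 98.7% depends on it only slightly. The documents give no placebo rates for Weeks 4 and 8 or for K16, so nothing is claimed there. The inconsistency between Protocol 9.4.4 and SAP 2.5.4 exists whatever the rate.

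**What to change.** 1. In SAP 2.5.4, name a weight-stratified risk difference as the supportive adjusted PASI 90 estimate: Mantel-Haenszel weights with a stratified Miettinen-Nurminen 95% interval. Report it at Weeks 4, 8 and 12 whether or not the logistic model can be fitted. It is on the same scale as the primary analysis and survives zero placebo responders. Firth logistic regression may be added under separation, with a note that its upper limit will say little. Because the cancel rule also covers K16, state whether the same estimate will be given for it.
2. State that by-stratum risk differences, with score intervals, are computed directly from the proportions as Protocol 9.4.4 describes, and not through the interaction model.
3. Replace the not-applicable entry in SAP Section 4 with a record of the cancel rule and any change to the by-stratum analysis.

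The primary analysis and sample size stay as they are. The cost is SAP text and a little programming, with no extra patients, visits or data. The supportive interval would on average be about 0.8 point wider in half-width than the unadjusted one without continuity correction (15.0 against 14.2 points at 56.2% against 1.15%, over 3,000 simulated trials).
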